- To estimate on a weekly basis the vaccine uptake among the subjects registered in the enrolled GP practices, by age strata (6 months to 5 years; 6 to 12 years; 13 to 17 years; \geq 18-65 years; $>$ 65 years) and CMO-specified risk groups.
- To assess the completeness of vaccination data in the EHR
- To assess the timeliness of availability of vaccination data in the EHR
- To evaluate the return rate of ADR cards
- To assess the timeliness of AEI reports in the EHR from medically attended AEIs and from the card-based ADR reporting system

- To assess the timeliness of generating weekly reports

Primary endpoint:

- Occurrence of AEIs (Appendix 2) within 7 days post vaccination reported using a card-based ADR reporting system overall, by age strata (6 months to 5 years; 6 to 12 years; 13 to 17 years; \geq 18-65 years; $>$ 65 years) and UK CMO-specified risk groups status (at risk/not at risk), each week and cumulatively, overall and by vaccine brand (*Fluarix Tetra* vs. others). AEIs will be presented by system organ categories.

Secondary endpoint:

- Occurrence of AEIs within 7 days post vaccination reported using data entered in EHR (i.e., AEIs derived from a card-based ADR reporting system and medically attended AEIs) overall, by age strata (6 months to 5 years; 6 to 12 years; 13 to 17 years; \geq 18-65 years; $>$ 65 years) and UK CMO-specified risk groups status (at risk/not at risk), each week and cumulatively, overall and by vaccine brand (*Fluarix Tetra* vs. others). AEIs will be presented by system organ categories.

Tertiary endpoints:

- Seasonal influenza vaccination status among the subjects registered in the enrolled GP practices, overall, by vaccine brand, by age strata (6 months to 5 years; 6 to 12 years; 13 to 17 years; \geq 18-65 years; $>$ 65 years) and UK CMO-specified risk groups and date of vaccine administration collected in the EHR system
- Level of missing data related to vaccination information (date of event, vaccine brand, vaccine batch).
- Lag time between date of vaccine administration and date at which vaccination record is encoded in the EHR system
- Return of ADR cards
- Time interval between AEI onset date and recording in the EHR by source (medically attended vs via ADR cards).
- Time interval between the date data extraction and date at which the weekly report is generated.

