10. APPENDIX

Appendix 1

Data extraction is by automated routine as detailed below:

Currently, data are extracted by weekly bulk upload. Apollo extracts data using the Apollo automated extraction system. Communication is via a SOAP (Simple Object Access Protocol) web service, no special firewall configuration is needed.

At the point of the data drop the data are filtered and processed through a pseudonymisation package encrypting the NHS number. All data are strongly encrypted by a combination of symmetric and asymmetric encryption algorithms: Triple DES and RSA 1024 before transmission, and utilises public and private key pairs unique to each project.

Pseudonymisation is applied at this stage to allow for backwards identification should there be a need to do so as part of an ethically approved study. However, the application of pseudonymisation at this stage also allows the same algorithm to be applied to additional data sources which may be linked data in future years; for example, enabling the linkage of patients' primary care and hospital data without the need to identify a person in the process of conducting this linkage.

Once the data are extracted, they are transferred using the above methodology to the custom built Data Warehouse located within University of Surrey for analysis in secure networks that meet the NHS Information Governance toolkit level 2 standard. These arrangements may change in the future in accordance with developments in technology.

Appendix 2 Code list of AEs**Project title: Post-authorisation passive enhanced safety surveillance of seasonal influenza vaccines: Pilot study in England– Preferred code list**

If a patient presents with adverse events post-vaccination (up to 7 days after), please code (ideally as a problem) as any of the following please code them into their computerised record

EMA surveillance condition	Read Code (5 Byte)	Read Code (CTV3)	Notes
Respiratory/Miscellaneous			
Conjunctivitis	F4C0.	XE16X	Sticky eyes
Rhinorrhoea	1C83.	XM00h	Runny nose
Nasal congestion	H1y1z	X77Gp	Blocked nose
Epistaxis	R047.	Xa96W	Nose bleed
Coryza	H00..	XE0XI	Common cold
Cough	171..	XM0Ch	
Oropharyngeal pain	1922.	1922.	Sore throat
Hoarseness	1CA2.	1CA2.	Hoarse voice
Wheezing	1737.	XE0qs	
Gastrointestinal			
Decreased appetite	R0300	XM07Y	
Nausea	198..	X75qw	Feeling sick
Vomiting	199..	XE0rA	Being sick
Diarrhoea	19F..	19F2.	
Fever/pyrexia			
Fever	165..	X76DI	

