Mild fever (<38.5°C rectal)			Please include level of temperature, to help us classify the fever
Moderate fever (38.6-39.5°C)	2E3..	2E3..	
High fever (>39.5°C)			
Sensitivity/anaphylaxis			
Hypersensitivity reactions	SN52.	Xa5uf	Allergic reaction
Anaphylactic reactions	SN501	X70vr	Other allergic reactions
Facial oedema	16J5.	Xa0ls	Facial swelling
Rash			
Rash	M130.	X50Ge	
Generalised rash	2I14.	XM07J	
General non-specific symptoms			
Irritability	225A.	225A.	
Drowsiness	1B67.	XM06R	
Fatigue	168..	1682.	
Headache	1B1G.	XM0CV	
Neurological			
Bell's palsy	F310.	F310.	
Peripheral tremor	1B22.	XE0rn	Tremor/shaking
Guillain-Barre Syndrome (GBS)	F3700	F3700	
Seizure/ Febrile convulsions	1B64.	XaDbE	
	1B6B.	XM03I	Seizure/ fits
Musculoskeletal			
Muscle aches/ myalgia	N2410	X75rs	
Arthropathy	N037.	X701f	Joint pain
Local Symptoms			
	SP3y4		
Local erythema	SP3y5	X75ty	Local reaction to vaccine
	SP3y6		
	SP3y7		

If a patient hands back an Orange Card with their symptoms – please code these and include the code 9G4.. (Drug reaction notification).

N.B.: In coding these conditions there is no assumption about causation; this can only come from advanced analytics.

Principal Investigator: [name]

Practice Liaison Officer: PPD

Project title: Post-authorisation passive enhanced safety surveillance of seasonal influenza vaccines: Pilot study in England– Preferred code list

If a patient presents with adverse events post-vaccination (up to 7 days after), please code (ideally as a problem) as any of the following please code them into the patients computerised record

EMA surveillance condition	Read Code (5 Byte)	Read Code (CTV3)	Notes
Respiratory/Miscellaneous			
Conjunctivitis	F4C0.	XE16X	Sticky eyes
Rhinorrhoea	1C83.	XM00h	Runny nose
Nasal congestion	H1y1z	X77Gp	Blocked nose
Epistaxis	R047.	Xa96W	Nose bleed
Coryza	H00..	XE0XI	Common cold
Cough	171..	XM0Ch	
Oropharyngeal pain	1922.	1922.	Sore throat
Hoarseness	1CA2.	1CA2.	Hoarse voice
Wheezing	1737.	XE0qs	
Gastrointestinal			
Decreased appetite	R0300	XM07Y	
Nausea	198..	X75qw	Feeling sick
Vomiting	199..	XE0rA	Being sick
Diarrhoea	19F..	19F2.	
Fever/pyrexia			
Fever	165..	X76DI	
Mild fever (<38.5°C rectal)			Please include level of temperature, to help us classify the fever
Moderate fever (38.6-39.5°C)	2E3..	2E3..	
High fever (>39.5°C)			
Sensitivity/anaphylaxis			
Hypersensitivity reactions	SN52.	Xa5uf	Allergic reaction
Anaphylactic reactions	SN501	X70vr	Other allergic reactions

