3.4. Data extract from EHR

The following data from subjects in the 10 enrolled GP practices will be imported (anonymised) into the secure servers of the University of Surrey:

- Demographic information: age, gender, ethnicity, date of registration
- Seasonal influenza vaccine information: date of administration, brand and batch number when available
- Postcode: to understand any inequities in access according to level of social deprivation using Geographical Information System (GIS) methods. Full postcodes will be immediately transformed into deprivation scores, using the Index of Multiple Deprivation (IMD), within GP computer systems upon extraction
- Primary care consultations following vaccination, any other markers of health care utilisation, and referral to further care.
- Pre-specified European Medicines Agency (EMA) adverse events of interest (AEIs) ([Annex 2](#)) or any other reported AE recorded in the EHR. Only coded data (Read code and CTV3), i.e. where the GP codes a disease or symptom into the EHR system, will be extracted
- Data from at least one year prior to the start of the study to determine the category of UK Chief Medical Officer (CMO)-specified risk group for influenza vaccination the subjects belong to:
 - Life-style/risk factors – e.g. body mass index, smoking status
 - Records of other diseases and long term conditions – e.g. chronic respiratory disease, chronic heart disease, chronic kidney disease, chronic liver disease, chronic neurological disease, diabetes, immunosuppression, pneumonia, etc
- Pregnancy status during the course of the study period

No individual patient level data will be released to GSK.

GSK will be blind to GP practice identities, and the locality at which any AE occurs.

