7.3.4. Analyses of tertiary objectives

The analysis on vaccine uptake is described in Section [7.2](#).

Completeness of seasonal influenza vaccination data in the EHR will be assessed by computing the percentage of subjects from the Cumulative vaccinated cohort Weeks 35-48 with data on influenza vaccines recorded in EHR, by Vaccine group:

- The denominator will be the number of subjects in the Cumulative vaccinated cohort Weeks 35-48
- The numerator will include all subjects from the denominator with the following respective data recorded in EHR:
 - Complete date of vaccination
 - Vaccine batch number
 - Both complete date of vaccination and vaccine batch number

Timeliness of vaccination data in the EHR will be assessed as follows:

- Time interval in days between the seasonal influenza vaccination dates and the dates at which the records were encoded in EHR will be summarized by Vaccine group using descriptive statistics (mean, standard deviation, median, range, first and third quartile) for the Cumulative vaccinated cohort Weeks 35-48. This time interval in days will also be graphically displayed.

Compliance in returning ADR cards is described in Section [7.3.1](#).

Timeliness of AEI reporting in EHR will be assessed as follows:

- Time interval in days between the first onset date of AEIs within the 7 days post-vaccination period and the dates at which the records were encoded in EHR will be summarized by Vaccine group and ADR cards returned status using descriptive statistics (mean, standard deviation, median, range, first and third quartile) for the Cumulative vaccinated cohort of Weeks 35-48. This time interval in days will also be graphically displayed.

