12.2. Data derivation

12.2.1. Date derivation

The date of birth will be modified during the extract from EHR to protect personally identifiable information. The modified date of birth will contain the exact month and year of birth of the subjects, but the exact day of birth will not be provided and will be set to '01' for all the subject's birth dates.

If the vaccine administration date is incomplete or missing the following rule will be applied:

- Day missing: 15 is used (standard GSK imputation)
- Month or year is missing: vaccination not included in the statistical analysis

If the start date of the AEI is incomplete or missing, a conservative approach (worst case scenario) will be used for imputation for the vaccinated subjects. The rules for imputation are detailed below, the examples are given assuming 16OCT2017 as date of vaccine administration.

- Day missing:
 - Month of onset = month of administration: day of administration will be used (e.g. OCT2017 → 16OCT2017)
 - Month of onset > month of administration: first day of the month will be used (e.g. NOV2017 → 01NOV2017)
 - Month of onset < month of administration: AEI not included in the statistical analysis
- Month or year missing: AEI not included in the statistical analysis

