14. ANNEX 3 ADVERSE DRUG REACTIONS SOLICITED IN THE CARD

Possible side effect or Condition in the 7 days after influenza vaccination	Start date of the symptom	Please tick as appropriate
Conjunctivitis – Sticky eyes	____/17	
Runny nose	____/17	
Blocked nose	____/17	
Epistaxis – Nose bleed	____/17	
Common cold	____/17	
Cough	____/17	
Sore throat	____/17	
Hoarse voice	____/17	
Wheezing	____/17	
Decreased appetite	____/17	
Nausea – feeling sick	____/17	
Vomiting – being sick	____/17	
Diarrhoea	____/17	
Fever (add temperature if measured)	____/17	
Allergic reaction (rash)	____/17	
Other allergic reactions	____/17	
Facial oedema (swelling)	____/17	
Local reaction to vaccine	____/17	
Rash	____/17	
Irritability	____/17	
Drowsiness	____/17	
Fatigue	____/17	
Tremor / shaking	____/17	
Seizure / fits	____/17	
Headache	____/17	
Muscle aches	____/17	
Joint pain	____/17	
Other		
1. _____	____/17	
2. _____	____/17	
3. _____	____/17	
Add below if more		

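### AEI reporting time by source cannot be interpreted until the plan says where the onset date of a medically attended AEI comes from; imputed onsets and a table by card-return status add to the problem

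*Protocol*

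**What the plan says.** - **Endpoint.** Protocol 4b (Tertiary endpoints), repeated in SAP 5.3: "Time interval between AEI onset date and recording in the EHR by source (medically attended vs via ADR cards".
- **Analysis.** SAP 7.3.4 starts the clock at onset without separating sources: "Time interval in days between the first onset date of AEIs within the 7 days post-vaccination period", ending when the record is encoded in the EHR. The results "will be summarized by Vaccine group and ADR cards returned status using descriptive statistics".
- **Card.** Protocol Appendix 3 and SAP Annex 3 give each symptom a field headed "Start date of the symptom".
- **Consultations.** Protocol Appendix 2 tells practices "please code (ideally as a problem) as any of the following please code them into their computerised record". It does not ask for an onset date.
- **Returned cards.** The same appendix says "please code these and include the code 9G4.. (Drug reaction notification". It does not ask for the start date to be transcribed.
- **Extract.** SAP 3.4: "Only coded data (Read code and CTV3), i.e. where the GP codes a disease or symptom into the EHR system, will be extracted". The Protocol section on data extraction and data management also rules out free text. Neither list names an AEI onset date.
- **Incomplete onset dates.** SAP 12.2.1, described there as a worst-case approach: "Month of onset = month of administration: day of administration will be used". A missing day in a later month becomes the first of that month. A missing month or year removes the AEI.
- **Weekly report.** SAP 9.1.1 issues each report 3 weeks after the week it covers, so that data can reach the EHR.

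**The concern.** An interval compared between two routes needs a start date that means the same thing in both. Here one route has a visible field for the start date. For the other, the readable text gives no origin for it. A difference between the sources could then come from how onset is obtained and not from how quickly AEIs reach the record.

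Two features of the SAP make this worse. The imputation rule suits incidence, where an early onset keeps an uncertain AEI inside the 7-day window. In a delay it adds days that did not occur. The grouping variable describes the subject and not the AEI, so the comparison named in SAP 5.3 is not the one tabulated in SAP 7.3.4.

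What is at stake is modest but not empty. Protocol 4b singles out completeness and timeliness as the focus of the data-quality evaluation, and Protocol 4a records that the first pilot did not deliver outcomes in near real time. The useful question is whether AEIs are in the EHR when the weekly report is produced. The planned table does not answer it.

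**Working it through.** The documents attach no timeliness figure to this endpoint, so there is nothing to reproduce. The check traces the onset date and then applies date arithmetic.

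**1. Where onset can come from, by source**

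| Step | Card | Medically attended |
|---|---|---|
| Field for symptom start | Yes (Protocol Appendix 3, SAP Annex 3) | None in the readable text |
| Instruction to enter it in the EHR | None seen (Protocol Appendix 2) | None seen (Protocol Appendix 2, SAP Annex 2) |
| Onset item in extract list | None named (Protocol 5a, SAP 3.4) | None named (same) |
| Free text as fallback | Not extracted | Not extracted |
| Rule if incomplete | SAP 12.2.1 | SAP 12.2.1 |

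**2. One medically attended AEI under each possible handling**

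Assumed case: vaccinated 16 October 2017 (the date in the SAP's own example), true onset 18 October, consulted and coded 22 October. Interval = recording date − onset date used.

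- True onset recorded: 22 − 18 = 4 days.
- Month known, day missing (SAP 12.2.1): onset becomes 16 October, so 22 − 16 = 6 days.
- Month or year missing (SAP 12.2.1): AEI excluded, no interval.
- Consultation date standing in for onset (not stated in either document): 22 − 22 = 0 days.

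The same AEI gives 0, 4 or 6 days, or drops out, according to a choice that the text does not make.

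**3. Size of the imputation error**

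SAP 7.3.2 counts the day of vaccination plus the following 7 days. Error = true onset − imputed onset.

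- Same month: imputed to day 0 and true onset on day 0 to 7, so the interval is overstated by 0 to 7 days.
- Later month: imputed to the first of that month. For vaccination on 31 October the window ends on 7 November, so the error is at most 7 − 1 = 6 days.

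Both bounds apply to AEIs whose true onset lies in the window.

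**4. Card-return status is not AEI source**

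Subjects who returned no card contribute only medically attended AEIs. Subjects who returned one contribute card AEIs and any consultation AEIs, so their row is a mixture. Protocol 4a reports a return rate of roughly 50% in the previous season. If consulting is assumed to be unrelated to returning a card, about half of the medically attended AEIs would sit in the returned row. Without that assumption the share could be anything from 0 to 100%.

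**5. Time available before the weekly report**

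Counting 3 weeks from the end of a full Monday-to-Sunday week, the report falls 21 days after a Sunday vaccination and 21 + 6 = 27 days after a Monday one. A card returned on day 14, the deadline in Protocol 5a, leaves 21 − 14 = 7 to 27 − 14 = 13 days for entry and extraction. A percentage recorded by that date bears directly on the reporting schedule. A mean delay from onset does not.

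**The case against.** A reader might go further and infer that the consultation interval is near zero by construction, that only the card collects an onset date, and that the comparison is therefore invalid. The documents do not support this.

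- Zero arises only if the consultation or coding date serves as onset, and no passage says so. The SAP treats onset and encoding as separate dates and assumes that a start date exists. When it is incomplete, SAP 12.2.1 leads to an earlier onset or to exclusion, not to zero.
- The absence of an onset field for consultations cannot be asserted. The data-capture flow charts, some appendix pages and the tables document are not available here, and an instruction could be in any of them.
- The extract lists are summaries. They name no AEI dates of any kind, although the analysis needs both onset and entry dates. By the same reading, the card's start date is not shown to reach the extract either.

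It can also be argued that starting the clock at vaccination measures something else, because it mixes time to symptom with reporting delay. That is fair and rules out substitution. It does not rule out adding the interval as a second measure.

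Finally, the analyses are descriptive and the endpoint is tertiary. That limits the importance of the point. It does not remove the mismatch between SAP 5.3 and SAP 7.3.4, or the imputed delays.

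**Conclusion.** The point holds in a limited form. The by-source timeliness comparison is not interpretable unless onset is obtained in the same way for both sources, and the readable text does not show that it is. Two further points can be read directly from the SAP: its general imputation rule overstates the delay by up to 7 days for an AEI with a missing onset day and true onset in the window, and the planned table classifies subjects instead of AEIs.

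How often onset is imputed or missing is unknown, so the overall effect on the reported medians and means cannot be sized. The conclusion rests on the readable text. If an onset instruction exists elsewhere, the first part is resolved by citing it, and the other two remain. This is a cheap improvement to a tertiary, descriptive endpoint, with no bearing on the incidence rates.

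**What to change.** In SAP 7.3.4:

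1. State the origin of the onset date for each source. Restrict the onset-based interval to AEIs with a complete, non-imputed onset date. Report per source the share of AEIs with onset recorded, imputed and missing.
2. Tabulate by AEI source, with card AEIs identified by the card notification code and the others as medically attended, in place of the subject's card-return status.
3. Add, without replacing the protocol's interval, the time from vaccination to EHR recording by source. Give the median, quartiles and percentage recorded by the weekly report date, 3 weeks after the vaccination week. Exclude records whose vaccination day was imputed to the 15th under SAP 12.2.1.
4. List the added interval in SAP section 10.

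The cost is SAP wording and one revised table. The vaccination and recording dates are already used in SAP 7.3.4, and the protocol endpoint stays as it is.

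The added interval has limits that should be stated with it. It includes up to 7 days before the symptom begins. The routes will also still differ, because cards may be returned up to day 14. It shows when information arrives, not which route is intrinsically faster.

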5. RESEARCH METHODS

a. Study Design

Study setting and population

Routinely collected primary care data from up to ten GP practices will be extracted, to support passive surveillance. Additionally, this passive surveillance will be enhanced by the use of a card-based ADR reporting system. ADR card will be distributed to patients and upon return entered into the EHR system.

EPI-FLU-055 VS UK study targets to follow vaccinated patients between 01/09/2017 and 30/11/2017.

A customized ADR card will be used, which lists pre-defined categories of AEIs to be reported, similarly to study EPI-FLU-046 (2016/2017 season). A field will also be included to report AEIs not listed as well as a field to indicate that no AEI occurred within the 7 days-time window. Patients will be provided with the ADR cards and asked to complete the ADR cards with any AEIs occurring within 7 days post vaccination and to return the cards to the GP practices not later than 14 days post-vaccination^{vii}.

GP practices ordering mainly GSK's *Fluarix Tetra* vaccine for the 2017/18 season will be contacted to inquire about their interest in participating in this study. This may also include existing research contacts and networks of the University of Surrey. GP practices selection will ensure distributed location across England (in London, a Northern city, and rural settings in the North and South) and that the participating population spans different age strata, different levels of deprivation, different ethnic mix, different brand of computerised medical record systems, and different practice sizes. However, this will be tempered by our need to recruit before the start of the influenza immunisation season.

GP practices will also be included based on their ability to comply with the protocol requirements (e.g., number of subjects registered, IT system used). GP practices will be reimbursed for their involvement in this study, according to the National Institute of Health Research (NIHR) guidelines for industry sponsored studies^{viii}.

Of note, regulatory compliance studies can be registered with the National Institute for Health Research (NIHR) Clinical Research Network (CRN) Portfolio^{viii}. Advice will be sought as to whether this study qualifies.

Inclusion criteria

1. Surveillance is planned to apply to vaccination between 1st September and 30th November 2017

As this is a GP sentinel safety surveillance study, all individuals who receive influenza vaccination in the 10 participating GP practices between 1 September and 30 November 2017 are planned to be eligible for inclusion in the analysis. A date of 30 November allows for safety evaluation and potential signal detection early in the annual vaccination period and was selected for the 2016/2017 season.

2. GP Practices primary vaccine supplier will be preferentially GSK

To fulfil its commitment, the Company will recruit from GP practices ordering preferentially GSK's *Fluarix Tetra*. Therefore, an inclusion criterion is that GP practices use GSK as their principal vaccine supplier.

Exclusion criteria

Data will not be extracted from patients having “opted out” in respect of use of their medical data

Registered patients who have explicitly opted out of data sharing will be excluded from the analysis. These patients will be identified by the opt-out codes within GP information systems. Patients will be informed of their option to opt-out via posters in the GP practices and information sheets accompanying the ADR cards.

Data extraction and data management

There are a number of GP EHR systems in use; the systems eligible for use in English primary care must be part of GP System of Choice (GPSoC)^{ix}. GP practices have a single EHR system, which contains comprehensive data about patients, their medical history including treatment and all the aspects of providing General Medical Services (GMS – the standard NHS primary care provision) or other primary care schema. There are predominantly 3 brands; the market leader is Egton Medical Information Systems (EMIS), followed by The Phoenix Partnership (TPP) SystmOne, and In Practice Systems (INPS) Vision.

Two data sources are considered for this study, i.e., the general practice EHR data (routine data collection) which provides the standard passive surveillance component and the ADR cards system completed by patients corresponding to the enhanced component. The ADR cards are being returned to the patient's own practice to ensure confidentiality. Using a specific code, the data from these cards will be also coded into the EHR and uploaded weekly.

1. General Practice EHR data recorded by the practice team. Weekly data about vaccine exposure, and any subsequent AEIs will be uploaded (anonymised) to University of Surrey. The EHR data contains both AEIs recorded by the practice team, as well as data reported to the GP practice on an ADR card by a vaccinated patient.
2. ADR cards completed by patients. Among the 10 participating GP practices, patients who are vaccinated against influenza will be provided ADR cards. These ADR cards customised following practice feedback to match EMA requirements will be used to collect AEIs reported after the receipt of influenza vaccination.

The method and governance procedure has been developed by the University of Surrey, using an approved provider, Apollo. If not applicable, alternatively, another approved data extraction supplier will be chosen, or the relevant study data will be directly extracted by the University of Surrey team using standard data extraction tools such as Morbidity Information Query Export Syntax (MIQUEST), tool sponsored by the Department of Health.

Data extractions will be conducted in accordance with the Research Group's standard operating procedures in data extraction, pseudonymisation, and transfer.

Pseudonymisation is a process that involves the removal of all personal identifiers – such as name, date of birth, etc. Furthermore, encrypted data will be kept during transfer and on a secure network that meets NHS Information Governance standards to minimise the risk of re-identification. Pseudonymisation is the standard approach for this type of surveillance. A legally binding definition of pseudonymisation has been introduced into European law^x on the recommendation of the European Data Protection Supervisor (EDPS)^{xi}.

Data are anonymised (strictly defined as “pseudonymised”) as near to source as possible. All data are strongly encrypted by a combination of symmetric and asymmetric encryption algorithms: Triple DES¹ and RSA 1024² before transmission, and utilises public and private key pairs unique to each project. Pseudonymisation is applied at this stage to allow for backwards identification should there be a need to do so as part of an ethically approved study.

For this study, it is required to link an adverse event to the vaccine (specific brand and batch number) administered. Pseudonymisation allows this without knowing any of the strong personal identifiers of that individual.

All data processing and analysis in the study will be conducted within the secure IT environment of the Clinical Informatics Research Group, at the University of Surrey. The information security policies and procedures of the Research Group have been approved by the NHS Digital as meeting Information Governance Toolkit (IGT) standards^{xii}.

The system is continuously being updated and modernized in respect of information processing, security and governance processes. The data are automatically extracted from the network of GP practices using a Simple Object Access Protocol (SOAP) web service, on a weekly basis. Data are uploaded to a secure Microsoft SQL server, and processed into aggregated tables; these are then linked to a pre-defined report structure using business intelligence software (Tableau Software, Inc. Seattle, WA, www.tableau.com), to produce a weekly surveillance report in a timely manner.

Using the EHR system, routine data as well as the content of encoded ADR cards will be extracted using methods that Surrey developed and deploys to extract RCGP RSC surveillance data. Sensitive coded data and free-text data will not be extracted. Only relevant EHR data for this study (e.g. disease or symptom, vaccination status and brand) coded by the GPs or other health professional will

¹ This is also referred to as “3DES”, which is the commonly used name for the triple data encryption algorithm (TDEA, also written Triple DEA) symmetric-key block cipher.

² RSA stands for Rivest, Shamir and Aldeman who founded RSA Laboratories. They created large numbers with only two prime factors, a core component of the encryption process

be extracted^{xiii}. Large volume of research that has come out of UK primary care is based on coded data^{xiv}. The quality of primary care data are such that the expectation will be able to detect frequent AEIs.^{xv}

GP practices will be required to use the relevant Read code for ADR notifications, when recording data from a returned card (Read Code: PPD - Adverse drug reaction notification).

Relevant coded data will be extracted, however these are limited to the administration regime, AEIs and batch number fields of prescribing data.

The following routinely collected patient data will be extracted for the study:

- Demographic information: age, gender, ethnicity, date of registration.
- Seasonal influenza vaccine information: date of administration, brand and batch number when available
- To understand any inequities in access according to level of social deprivation using Geographical Information System (GIS) methods, full postcodes will be immediately transformed into deprivation scores, using the Index of Multiple Deprivation, within GP computer systems upon date extraction.
- Primary care consultations following vaccination, any other markers of health care utilisation, and referral to further care.
- AEIs (Appendix 2) or any other reported AE recorded in the EHR.
- Data from at least one year prior to the start of the study to determine the category of UK CMO-specified risk group for influenza vaccination the subjects belong to:
 - Life-style/risk factors, CMO risk status – e.g. BMI, smoking status.
 - Records of other diseases and long term conditions – e.g. chronic respiratory disease, chronic heart disease, chronic kidney disease, chronic liver disease, chronic neurological disease, diabetes, immunosuppression, pneumonia, etc.
 - Pregnancy status during the course of the study period.

Sample size consideration

The average practice size in England is 7,034 patients^{xvi}, an estimate of approximately 70,340 patients are expected to be registered (across the ten participating GP practices). Of note, in the period from September to December 2016, the seasonal influenza vaccine uptake for over 65 year olds was 71.0%; for those in a clinical risk group aged 6 months to 65 years old, the uptake was 45.1%; and for pregnant women, it was 42.3%. The estimate of influenza vaccine uptake had been made estimated using the coverage estimates published by Public Health England (PHE)^{xvii}.

The eligible target population to be medically followed by the GPs would be estimated at 50,000 subjects (approximately 5,000 per practice using a conservative approach). As per EMA Pharmacovigilance Risk Assessment Committee (PRAC)/Vaccine Working Party (VWP) request, at least 1,000 vaccinated subjects with 7 days of follow-up after vaccination are targeted to be enrolled. In this study, up to 5,000 vaccinated subjects with 7 days of follow-up after vaccination are expected to be enrolled. This sample size estimation sets out to estimate the probability to observe at least

one AEI in the study population and evaluate the level of "certainty" around this finding; over a 14 week-surveillance period (01 September – 30 November 2017).

The recruitment will be performed by GP practice and this might create a clustering effect. Based on the previous year study (EPI-FLU-046 study) the clustering effect is expected to be negligible. Similarly to last year, in the present study, the clustering effect was not accounted for in the power calculation but will be considered during the analysis.

Cluster effect

Cluster effect requires special statistical considerations when designing the study, and later when analysing the data. Groups tend to form because of certain selection factors, so individuals within the group tend to be more similar to each other with respect to important potential confounders than those selected truly at random.

For instance, patients medically followed by the same GP are usually more prone to receive similar treatment for a given condition than those being treated for the same condition by different physicians. Furthermore, patients attending a single GP practice are likely to share similarities including geography, socioeconomic status, ethnic background, or age by virtue of the area they have all chosen to live in the same way. GPs who have chosen to work together are likely to share similarities.

Similarities, or homogeneity, between subjects in clusters reduces the variability of their responses, compared with that expected from a random sample. As a consequence, a compensatory increase in sample size is required to maintain power in studies characterised by a cluster effect and the degree of similarity of within clusters should also be assessed. The intra-cluster correlation coefficient (ICC) is a measure of the relatedness or similarity of clustered data. There are different methods of calculating the ICC, usually requiring a pilot study, but all compare the variance within clusters with the variance between clusters.

Sample size calculation

Table 1 shows the exact 95% CI, the probability of observing at least one AEI during the study period in the study cohort and the relative standard error (RSE) for a range of scenarios in term of cohort size, vaccine coverage and expected probability of AEI^{xviii}. With an overall cohort size of about 50,000 subjects medically followed by the participating GP practices, an estimated study period of 14 weeks, a vaccine coverage of 2%, 5%, 10% or 20% and an expected probability of AEI varying from 0,01% to 20%, the corresponding probability to observe at least one event in our study population varies from 9 to >99%, and the associated relative standard error varies from 2.0% to 316% depending on the scenario.

Table 2 shows the evolution by week of the exact 95% CI, the cumulative probability of observing at least one AEI in the study cohort and the relative standard error (RSE) in the course of the study for a range of scenarios in term of cohort size, vaccine coverage and probability of AEI of 1%. With an overall sample size of a minimum of about 50,000 subjects medically followed by the enrolled GP practices, a follow-up period of 14 weeks, a vaccine coverage of 2%, 5%, 10% or 20%, the

corresponding cumulative probability to observe at least one event in our study population varies from 51% to 100% after week 1, and the associated relative standard error varies from 9% to 118% depending on the scenario.

Table 1

Exact 95% Confidence Intervals, Relative Standard Error and probability to observe at least one AEI according to expected probabilities of occurrence of AEIxix

Expected Population medically followed by the enrolled practices	Vaccine coverage	Vaccinated subjects	Subjects with events	Expected Proportion of subjects with ≥1 AEI reported	Lower 95%CL	Upper 95%CL	Probability to observe ≥1 AEI in the study population	Associated Relative standard error (RSE)
50000	20%	10000	2000	20.00%	19.2%	20.8%	>99.99%	2.0%
50000	20%	10000	1500	15.00%	14.3%	15.7%	>99.99%	2.4%
50000	20%	10000	1000	10.00%	9.4%	10.6%	>99.99%	3.0%
50000	20%	10000	500	5.00%	4.6%	5.4%	>99.99%	4.4%
50000	20%	10000	400	4.00%	3.6%	4.4%	>99.99%	4.9%
50000	20%	10000	200	2.00%	1.7%	2.3%	>99.99%	7.0%
50000	20%	10000	100	1.00%	0.8%	1.2%	>99.99%	9.9%
50000	20%	10000	10	0.10%	0.0%	0.2%	>99.99%	31.6%
50000	20%	10000	9	0.09%	0.0%	0.2%	99.99%	33.3%
50000	20%	10000	8	0.08%	0.0%	0.2%	99.97%	35.3%
50000	20%	10000	7	0.07%	0.0%	0.1%	99.91%	37.8%
50000	20%	10000	6	0.06%	0.0%	0.1%	99.75%	40.8%
